18. Women of childbearing potential (WOCBP) (i.e., physiologically capable of becoming pregnant) who are unwilling or unable to use a highly effective method of contraception, (see Protocol Appendix 2) for the duration of the study, OR Men physiologically capable of fathering a child who are sexually active with WOCBP but are unwilling or unable to use barrier contraception (e.g., condom with or without spermicidal cream or jelly) for the duration of the study. NOTE: See Protocol Appendix 2 for definitions of WOCBP and highly effective methods of contraception and for information about unacceptable methods of contraception.
19. Women who are currently pregnant or breastfeeding or plan to become pregnant or breastfeed during the study.
20. Men who plan to donate sperm during the study.
21. Use of weight loss drugs [REDACTED] of screening until the end of study.
22. Subjects who are either unable or unwilling to consume alcohol in any amount (including due to religious or personal reasons).
23. Subjects who have a change in AISRS score of  $\geq 13$ -points between screening and baseline visits.

The baseline visit will occur on the clinic day before Day 1 and will confirm AISRS score. If there is a  $\geq 13$ -point change in the AISRS between the screening visit assessment and the baseline assessment, or if the subject does not return for the baseline AISRS, the subject will not be randomized, and will be terminated from the study. Eligible subjects will be randomized at Day 1 to either 20  $\mu$ g of MM-120 or to matching placebo and begin the double-blind treatment period on Day 1.

[figure not shown]
Double-blind treatment period:

The double-blind treatment period will last 6 weeks, with dosing twice weekly (every 3 to 4 days). Day 1 will be the first day of dosing. At the end of the 6 weeks-treatment period, subjects will be assessed by a study physician. All subjects and site staff will remain blinded to the treatment group.

Subjects will be provided with a diary in which the sleep quality/ duration rating data will be recorded.

Follow-up:

There will be a single follow-up visit 4 weeks after the last double-blind treatment visit (i.e., at Week 10).

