### **2.1.3 Visit windows**

As subjects do not always adhere to the protocol visit schedule, the following rules will be applied to assign actual visits to analysis visits for all parameters.

The visit windows and the target days for each visit (including unscheduled ones) are listed below in Table 2. The reference day is Day 1, the first day of dosing, as defined in Section 11.1.1. If a subject has two or more actual visits in the same visit window, the visit closest to the target day will be used for recording data from that visit in the EDC. The data collected scheduled and unscheduled visit(s) will be mapped to visits as follows: If two actual visits are equidistant from the target day within a visit window, the later visit will be used; if more than one value falls on the same day then the last sequential number in sdtm will be used.

All assessments corresponding to both scheduled and unscheduled visits will be included in subject listings.

Table 2 contains analysis visit windows and the target study days for the following selected visits: Baseline, Week 2, Week 4, Week 6 and Week 10; lower and upper limits associated with each visit will cover all possible days from randomization to end of study allowing mapping all the applicable assessments to the visits.

As vital signs and Columbia-Suicide Severity Rating Scale (C-SSRS) will be evaluated at each visit (twice weekly), a different time windowing will be applied to those variables only (see Table 3). Daily diary contains daily sleep quality/ duration rating assessments that will be computed at each week by the mean of values recorded between lower and upper limits (days) specified in Table 4, no target study day will be considered.

For parameters, where Time Interval Upper Limit for Baseline is equal to 1, please apply a rule of time defined in section 11.1.1.8 for Baseline.

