**Table 2: Scheduled Visit Window and Mapping of Assessments**

Assessment	Scheduled Visit Number	Scheduled Time point	Label on output	Target Study Day*	Time Interval Lower Limit (Day*)	Time Interval Upper Limit (Day*)
laboratory	Baseline	Baseline - Week 1D1	Baseline	1	No Lower limit	1
	Week 2	Week 1D5- Week 3D19	Week 2	15	2	21
	Week 4	Week 4 D22- Week 5 D33	Week 4	29	22	35
	Week 6	Week 6 D36 - Week 6 D40	Week 6	43	36	EOT
	Week 10 Follow-up/ Final visit for withdrawals	Week 10 Follow-up/ Final visit for withdrawals	Week 10 Follow-up/ Final visit for withdrawals	70	EOT+1	No Upper limit
Physical examination, ECG	Baseline	Baseline - Week 1D1	Baseline	1	No Lower limit	1
	Week 6	Week 6 D36 - Week 6 D40	Week 6	43	2	EOT
	Week 10 Follow-up/ Final visit for withdrawals	Week 10 Follow-up/ Final visit for withdrawals	Week 10 Follow-up/ Final visit for withdrawals	70	EOT+1	No Upper limit
Pregnancy test	Baseline	Baseline - Week 1D1	Baseline	1	-24	1
	Week 2	Week 1D5- Week 3D19	Week 2	15	2	21
	Week 4	Week 4 D22- Week 5 D33	Week 4	29	22	EOT
	Week 10 Follow-up/ Final visit for withdrawals	Week 10 Follow-up/ Final visit for withdrawals	Week 10 Follow-up/ Final visit for withdrawals	70	EOT+1	No Upper limit
Questionaries						
ASRS, CAARS-L-SR	Baseline	Baseline - Week 1D1	Baseline	-1	No Lower limit	-1
	Week 2	Week 1D5- Week 3D19	Week 2	15	2	21
	Week 4	Week 4 D22- Week 5 D33	Week 4	29	22	34

	Week 6	Week 6 D36	Week 6 D36	36	35	38
	Week 6	Week 6 D40	Week 6 D40	40	39	EOT
	Week 10 Follow-up/ Final visit for withdrawals	Week 10 Follow-up/Final visit for withdrawals	Week 10 Follow-up/ Final visit for withdrawals	70	EOT+1	No upper limit
AISRS, CGI	Baseline	Baseline	Baseline	1	No Lower limit	1
	Week 2	Week 2 D8	Week 2	8	2	21
	Week 6	Week 6 D40	Week 6	40	35	EOT
	Week 10 Follow-up/ Final visit for withdrawals	Week 10 Follow-up/Final visit for withdrawals	Week 10 Follow-up/ Final visit for withdrawals	70	EOT+1	No upper limit
Pharmacodynamics: SD-ASC**, MEQ- 30**, VAS***	Week 1 D1	Week 1 D1	Week 1 D1	1	NA	5
	Week 6	Week 6 D40	Week 6	40	NA	No upper limit

\* Relative to Study Day 1

\*\*No baseline assessment, post-dose at Week 1 D1

#No assessment at Week 6, only at visit Week1 D1 post-dose

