### **11.1.1.8 Baseline value**

Except where otherwise specified, baseline is defined as the last value measured or assessed before or on the date of the first dose of investigational drug administration at Visit 1. If the baseline visit takes place on the date of the first dose of investigational drug, then time should be considered, i.e. baseline date/time < first dose date/time.

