### 13.1.10 Layout T10

Study MMED007 - Deliverables: <Deliverables>

Table <Number of table>

<Title>

Analysis set: <analysis set>

Score: 

Visit

	MM-120 N=xx*	Placebo N=xx*
--	-----------------	------------------

Baseline

n	xx	xx
Mean	xx.x	xx.x
Standard deviation	xx.x	xx.x
Median	xx.x	xx.x
Q 1 , Q 3	xx.x, xx.x	xx.x, xx.x
Min, Max	xx.x, xx.x	xx.x, xx.x

Week <n>

n	xx	xx
Mean	xx.x	xx.x
Standard deviation	xx.x	xx.x
Median	xx.x	xx.x
Q 1 , Q 3	xx.x, xx.x	xx.x, xx.x
Min, Max	xx.x, xx.x	xx.x, xx.x

Change from Baseline to Week <n>

n	xx	xx
Mean	xx.x	xx.x
Standard deviation	xx.x	xx.x
Median	xx.x	xx.x
Q 1 , Q 3	xx.x, xx.x	xx.x, xx.x
Min, Max	xx.x, xx.x	xx.x, xx.x

Program: [program\\_name.sas](#), Produced on yyyy-mm-dd hh:mm (CET),

Snapshot date: yyyy-mm-dd, Draft/final

Page x of x

Note for programmer: Table will be presented by week: only subjects with both the baseline and specific time point assessment will be included.  refer to scores on 'Patient Reported Outcomes' eCRF page to be summarized in the table. In the table scores  should be reported as: A=Inattention/Memory Problems; B=Hyperactivity/Restlessness;

C=Impulsivity/Emotional Lability; D=Problems with Self-Concept; E=DSM-IV Inattentive Symptoms; F=DSM-IV Hyperactive-Impulsive Symptoms; G=DSM-IV ADHD Symptoms Total; H=ADHD Index.

Visit:

For scores ASRS and CAARS-L-SR: Week 2, Week 4, Week 6.

For scores AISRS and CGI-S: Week 2, Week 6.

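### SAP Table 2 leaves Day 1 outside every ASRS/CAARS-L-SR window and does not define a single Week 6 record for these scales

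*SAP*

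**What the plan says.** SAP 2.1.3 introduces the analysis windows with the statement that "lower and upper limits associated with each visit will cover all possible days from randomization to end of study". Randomization is on Day 1: "Eligible subjects will be randomized at Day 1" (SAP 2.1.1, after the exclusion criteria).

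In Table 2 the ASRS/CAARS-L-SR baseline row carries the time point Baseline - Week 1D1, but both its target day and its upper limit are Day -1. The laboratory baseline row has the same time point and reads "Baseline - Week 1D1 Baseline 1 No Lower limit 1", so its upper limit is Day 1. The AISRS/CGI baseline row also ends at Day 1. The next ASRS/CAARS-L-SR row is "Week 1D5- Week 3D19 Week 2 15 2 21", which opens on Day 2.

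The general baseline definition in SAP 11.1.1.8 takes the last value before or on the first-dose date, unless specified otherwise, and adds: "If the baseline visit takes place on the date of the first dose of investigational drug, then time should be considered". SAP 8.1.2 lists ASRS and CAARS-L-SR among the baseline characteristics and points to 11.1.1 for the definition.

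For Week 6, Table 2 gives these scales two rows, both under scheduled visit Week 6: "Week 6 D36 Week 6 D36 36 35 38" and "Week 6 D40 Week 6 D40 40 39 EOT". The analysis in 10.8.2.2 is at Weeks 2, 4 and 6, and the programmer's note to Layout T10 reads: "For scores ASRS and CAARS-L-SR: Week 2, Week 4, Week 6".

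**The concern.** The SAP gives two answers for a self-report form completed before dosing on Day 1. Section 11.1.1.8 accepts it as baseline; Table 2 has no window for it. Section 2.1.3 invokes the clock-time rule only for parameters whose baseline upper limit is 1, so that pointer does not reach ASRS or CAARS-L-SR.

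There is no substitute baseline. ASRS is not collected at screening, and the CAARS form used there is the observer-rated version. Section 11.3.2 rules out imputation for these endpoints, and Layout T10 keeps only subjects with both a baseline and a visit value.

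For Week 6, the nearest-to-target rule in 2.1.3 works within one window. It cannot choose between a D36 record and a D40 record, and neither label appears in the ASRS or CAARS outputs. Two competent programmers could therefore report different Week 6 Ns and means.

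**Working it through.** **Coverage.** The plan's own figure is full coverage from randomization to end of study. The ASRS/CAARS-L-SR windows in Table 2 are:

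| Output label | Lower day | Upper day |
|---|---|---|
| Baseline | none | -1 |
| Week 2 | 2 | 21 |
| Week 4 | 22 | 34 |
| Week 6 D36 | 35 | 38 |
| Week 6 D40 | 39 | EOT |
| Week 10 | EOT+1 | none |

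SAP 11.1.1.6 has no Day 0, so Day -1 is followed by Day 1. Every study day from -28 to 74 was assigned to these windows for an end of treatment (EOT) on Day 38, 40 or 43 (illustrative values). Each time exactly one day, Day 1, was uncovered, and no day fell in two windows. The stated coverage is therefore not reproduced. The laboratory rows of Table 2 and the windows in Tables 3 and 4 showed no gap under the same check.

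**Same visit, different treatment.** Protocol 6.2.2 puts AISRS, CGI-S, ASRS and CAARS-L-SR at one baseline visit. If that visit falls on Day 1 before dosing, AISRS and CGI-S map to baseline, and ASRS and CAARS-L-SR map to nothing.

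**Size per affected subject, on the literal reading.** One ASRS score plus eight CAARS-L-SR scores (A to H in Layout T10), at three visits: (1 + 8) × 3 = 27 change values.

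**Effect on precision.** Suppose k subjects drop out of one arm of 26, the other arm stays complete and the SDs are equal. The standard error of the difference is then multiplied by sqrt(1/(26−k) + 1/26) / sqrt(2/26):

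- k = 1: sqrt(0.07846/0.07692) = 1.010, an increase of 1.0%
- k = 2: sqrt(0.08013/0.07692) = 1.021, an increase of 2.1%
- k = 4: sqrt(0.08392/0.07692) = 1.044, an increase of 4.4%

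These values of k are assumptions, because the documents do not say how many baseline forms are dated Day 1.

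**Week 6.** Days 35 to EOT are fully covered, so no Week 6 score is unmapped. A form on Days 39 to 41 (nominal Day 40 ± 1) is labelled D40; a form on Day 37 or 38 is labelled D36. Twelve doses have 11 intervals. At an average of 3.5 days the last dose falls on Day 1 + 11 × 3.5 = 39.5, and uniform spacing of 3 or 4 days would give Day 34 or Day 45. A final-dose visit on Day 37 or 38 is therefore possible. AISRS from a Day 37 visit is labelled Week 6, while ASRS from that visit is labelled Week 6 D36.

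**The case against.** The best reply on baseline is that the SAP already has a governing rule. Section 8.1.2 ties these two scales to 11.1.1, and 11.1.1.8 accepts a pre-dose value on the first-dose date, so the Day -1 limit is a slip that a careful programmer would override. The schedule also places both forms at the Day -1 baseline visit and lists neither on Day 1, so the gap matters only for an off-schedule form. This largely stands, and it limits the practical risk. It does not remove the conflict. The exception clause in 11.1.1.8 lets Table 2 override the general definition, and 11.1.1.8 itself foresees a baseline visit on the dosing date.

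On Week 6, the schedule has one Week 6 assessment, before the final dose, and the last dose is at D40. That makes D40 the natural record, and both rows sit under scheduled visit Week 6. This also carries weight, but it does not say what to do with a form labelled D36, including one from a final-dose visit on Day 37 or 38.

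A reader might infer that self-report baselines and Week 6 scores will be lost. The documents do not support that. Baseline loss needs both a Day 1 form and a literal reading of Table 2. Week 6 loss needs a program that matches only the literal label Week 6 or keeps D40 alone. Nor do the documents support a claim that any loss would be non-random: baseline precedes randomization, so its date cannot depend on the assigned arm, and clustering by site is conjecture.

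**Conclusion.** The SAP is wrong as written on two details. Day 1 is in no ASRS/CAARS-L-SR window, against the coverage statement in 2.1.3, the row's own time point and the baseline definition in 11.1.1.8. And these scales have two Week 6 labels where the analysis needs one, with no selection rule.

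The severity is minor. ASRS and CAARS-L-SR are summarized descriptively, with no test and no gatekeeping role. The 27 values are a count for one assumed subject under the literal reading, and the precision figures rest on assumed losses in one arm. The number of subjects affected is not in the documents.

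Two broader inferences should be resisted. The primary AISRS analysis is not affected: its baseline limit is Day 1 and it has one Week 6 label. And these are not the trial's only self-rated efficacy measures, because the sleep diary is also self-rated.

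**What to change.** Change the ASRS/CAARS-L-SR baseline upper limit in Table 2 from Day -1 to Day 1, and state that the pre-dose time rule of 11.1.1.8 applies.

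Define one Week 6 record for these scales in either of two ways:

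- Merge the two rows into one window labelled Week 6, from Day 35 to EOT with target Day 40, and use the existing nearest-to-target rule.
- Keep both rows, name the one that feeds the Week 6 summary, and say how a form found only in the other is handled.

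With the Day 1 limit and the merged row, the same day-by-day check gives no uncovered days and no overlaps at EOT 38, 40 and 43, and one Week 6 record per subject with a form in that window. The cost is an edit to the baseline and Week 6 rows of Table 2 and the matching lines of the windowing program. No data collection changes.

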### 10.7.2 Main analysis

#### 10.7.2.1 Estimand

The primary estimand quantifies the treatment effect of MM-120 at 6-weeks vs placebo after twice weekly administration while accounting for intercurrent events (IEs) with potential confounding effects and IEs leading to study discontinuation prior to the 6-week assessment.

The following attributes describe the primary estimand:

- Population: Subjects in the FAS
- Endpoint: Change from baseline to Week 6 in the AISRS Score
- Treatment of interest: the randomized treatment MM-120 or placebo as a twice weekly treatment.
- Handling of intercurrent events (IEs) prior to AISRS assessments.

Depending on the IE causing the missing or potentially biased value, two sequential policy strategies will be applied:

1. Policy strategy. Available data will be used; missing data will be imputed under a Missing At Random (MAR) assumption by borrowing information from subjects in the same treatment group in following cases:
  - IEs related to COVID-19 pandemic and other intercurrent missing data (see details in Section 10.7.2.1.1).
2. Policy strategy. Available data recorded after the IE will be set to missing; such missing data will be imputed/substituted under a Missing Not At Random (MNAR) assumption by borrowing information from the placebo arm subjects (reference-based imputation) in following cases:
  - Intake of prohibited medications/therapies with potential confounding effect (APPENDIX C) (see details in Section 10.7.2.1.1).
  - Other IEs leading to treatment/study discontinuation (except those related to COVID-19 pandemic (see details in Section 10.7.2.1.1)).

- Summary measure: Difference between MM-120 and placebo in mean change from baseline to Week 6 for AISRS Score.

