#### **10.7.2.2 Analysis details**

Primary endpoint, change in AISRS score from baseline to Week 6, will be analyzed applying Rubin's rule to a multiple imputations procedure to appropriate contrasts based on Mixed Model for Repeated Measures (MMRM) analysis of covariance with the change in the AISRS score from baseline to Week 2 and Week 6 visits as dependent variable, and treatment group, visit, visit-by-treatment group interaction, baseline score of AISRS, sex and age as fixed effects. An unstructured variance-covariance matrix will be used to model within-subject errors. Satterthwaite's method will be used to approximate the degrees of freedom. If convergence problems arise (even just in one imputed dataset) the following order of matrices will be applied: Heterogeneous TOEP (TOEPH), Toeplitz (TOEP), Autoregressive(1) (AR(1)). The same variance-covariance matrix will be used in sensitivity analyses.

The imputation model include the longitudinal sequence of AISRS Scores, and the covariates used in the model as defined above. As a general approach, imputations are performed on observed values specifying a minimum and a maximum threshold (zero and 54 respectively) for AISRS. The change from baseline in AISRS Scores will not be imputed to avoid imputation of nonsensical values. For the imputation of missing data of AISRS, one thousand (1000) data sets will be generated, and the random seed number will be 200208. MI will be implemented following the steps below:

1. Imputation assuming a MAR (policy strategy 1).

MAR will be applied following the steps below:

- a)all assessments that took place after the IEs related to COVID-19 pandemic will be kept in the database;
- b)imputing all missing values already present in the data.

MI will be carried out based on fully conditional specification method (FCS, the details will be provided in the 'Programming standards and conventions' document). These datasets will be utilized in Step #2.

2. Imputation assuming MNAR (policy strategy 2).

MNAR will be applied following the steps below:

- a)assigning missing values to all assessments that took place after the IEs specified in policy strategy 2 above;
- b)imputing missing values assigned at step (a).

MNAR assumption based on copy reference approach (i.e. using the non-missing values of the placebo arm) will be used.

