### **11.1.1.3 Study treatment end date (EOT)**

This is the last day of study drug intake, which is the date reported in “Date of visit” field in section “Medical Events checks” (for each Visit form) when “LSD / Placebo administered” is ticked “Yes” in “Study Drug Administration” section.

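### SAP Table 2 closes the Week 6 AISRS/CGI-S window at the last dose taken, so a Week 6 rating after a missed dose 12 drops out of the Week 6 analyses; separately, Day 1 post-dose ECG, BP and HR have no summary window

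*SAP*

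**What the plan says.** **Windows.** SAP 2.1.3 assigns actual visits to analysis visits by study day, for all parameters, and states that the limits "will cover all possible days from randomization to end of study allowing mapping all the applicable assessments to the visits". Where two visits share a window, "the visit closest to the target day will be used for recording data from that visit in the EDC". For AISRS and CGI-S, Table 2 gives Week 2 as Days 2 to 21 (target Day 8) and Week 6 as Day 35 to EOT (target Day 40). The row "Week 10 Follow-up/ Final visit for withdrawals" runs from EOT+1 with no upper limit (target Day 70). SAP 11.1.1.3 defines EOT: "This is the last day of study drug intake".

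**Primary analysis.** SAP 10.7.2.2 fits the MMRM "with the change in the AISRS score from baseline to Week 2 and Week 6 visits as dependent variable". Step 1(b) of the imputation is "imputing all missing values already present in the data". Policy strategy 1 in SAP 10.7.2.1 reads "Available data will be used; missing data will be imputed under a Missing At Random (MAR) assumption". A missed dose is not among the intercurrent events in SAP 10.7.2.1.1. The programmer's note to Layout T10 limits the descriptive change table: "For scores AISRS and CGI-S: Week 2, Week 6".

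**Day 1 safety.** Protocol 6.2.3 plans an ECG 2 hours after the first dose and blood pressure and heart rate over 6 hours. SAP 2.1.3 and 11.1.1.8 admit only pre-dose Day 1 values as baseline. In Tables 2 and 3 the next ECG and vital-sign windows open on Day 2.

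**The concern.** EOT is the actual last dose, not planned Day 40, so the Week 6 window shrinks when the final dose is missed. A rating made at the intended visit, by a subject still in the study, then becomes a Week 10/Final value. It enters no AISRS model or summary table and survives only in the listing. The primary analysis fills the empty Week 6 cell by imputation although the score was observed. The complete-case MMRM (SAP 10.7.3.3) loses it outright. The Week 6 CGI-S improvement proportions (SAP 10.8.2.1) use non-missing scores without imputation (SAP 11.3.2), so they lose that subject too.

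The case is foreseen: the compliance shell (Layout T11) has a row for 11 of 12 doses.

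Two further consequences follow from the same tables. The coverage statement is untrue for AISRS/CGI-S, so some ratings have no analysis visit and others have two. And Protocol 7.4.1 says that first-dose blood pressure and heart rate are measured to show that there is no relevant effect, yet no planned table presents those readings by arm.

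**Working it through.** No design figure enters this check. The inputs are the Table 2 and Table 3 limits, the EOT definition, the nearest-to-target rule and the Day 1 time rule. The first row below is the reference case, which maps as the SAP intends.

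**Step 1: map AISRS/CGI-S ratings.** Current rule: Week 2 = Days 2–21, Week 6 = Day 35 to EOT, Week 10/Final = EOT+1 onward. Proposed rule, for subjects who have not withdrawn or discontinued: Week 6 = Day 35 to max(44, EOT), Week 10 from the next day.

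| Case | EOT | Rated | Table 2 as written | Proposed |
|---|---|---|---|---|
| Rated and dosed at the same visit | 40 | 40 | Week 6 | Week 6 |
| Dose 12 missed, dose 11 on Day 36 | 36 | 40 | Week 10/Final | Week 6 |
| Final dosing visit delayed to Day 45 | 45 | 45 | Week 6 | Week 6 |

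With dose 12 missed, dose 11 on Day 35, 36 or 37 and the rating on Day 39, 40 or 41, all 3 × 3 = 9 combinations map to Week 10/Final.

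**Step 2: follow the displaced rating.** With a follow-up on Day 68, the distances to target are |70 − 68| = 2 and |70 − 40| = 30. With a follow-up on Day 64 the first is 6. The Day 40 rating loses either way. Without a follow-up it becomes the Week 10/Final value, which no AISRS model or change table uses. Week 6 is then empty and step 1(b) imputes it.

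**Step 3: size.** One case is 1/52 = 1.9% of primary values, or 1/26 = 3.8% of an arm.

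**Step 4: coverage.**
- Gap: EOT of Day 34 or later leaves Days 22–34 without a window, 34 − 22 + 1 = 13 days. EOT of Day 22 to 33 leaves Day 22 to EOT without one.
- Overlap: for EOT of Day 20 or earlier, Week 2 and Week 10/Final share Days EOT+1 to 21, that is 21 − EOT days. For EOT on Day 1, 5, 8, 12, 15 or 19 this gives 20, 16, 13, 9, 6 or 2 days.
- Example: with EOT on Day 5, a scheduled Day 8 rating belongs to both windows, and no rule chooses.

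**Step 5: Day 1 safety.** A post-dose Day 1 value fails the baseline time rule. The next window starts on Day 2 for ECG (Table 2, Week 6 row) and for vital signs (Table 3, Days 2–6), so none holds it. Two post-dose ECGs are planned per subject (Day 1 and Week 6), 52 × 2 = 104 in all, and the 52 on Day 1 have no summary row. The number of Day 1 blood pressure and heart rate readings is not stated.

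**The case against.** **The case is narrow.** Protocol 6.2.4.4 schedules the rating before the final dose at the same visit. If that visit is late but the dose is given, EOT moves with it. This stands: the clear defect is confined to a missed final dose in a subject who stays and is rated.

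**The coverage gap is largely theoretical.** No AISRS or CGI-S is scheduled between the Week 2 and Week 6 ratings. This also stands: the gap reaches only unscheduled or early-termination ratings. The overlap is different, because after an early last dose it can catch a scheduled Week 2 rating.

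**Day 1 values are not lost.** Vital signs and ECG are listed for both arms (Layouts L11 and L25), and adverse events after dose 1 are tabulated. Protocol 7.4.1 asks for measurement rather than a table, Protocol 13.6.7.2 asks for summaries only where applicable, and SAP 8.11.5 and Layout T23 name only Baseline and Week 6 for ECG. Against this, SAP 10.12.3 promises ECG summaries at each time point. Listing L26, which sets blood pressure and heart rate beside the PK times, excludes placebo subjects.

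**Stronger readings that the documents do not support:**
- A reader might infer that every subject who stops dosing but is still rated wrongly loses a value. Strategy 2 sets ratings after treatment discontinuation to missing and imputes them by reference to placebo. SAP 10.7.2.1.1 confirms such events only through an adverse-event action, which leaves other stops unclear, but that does not show that their ratings belong in the MMRM.
- A reader might cite COVID-19 stops as a second clear case. SAP 10.7.2.1.1 item 1 assigns missing values after the event, while step 1(a) of 10.7.2.2 keeps the assessments. The text conflicts, so the example proves nothing.
- A reader might count early-withdrawal visits as mislabelled. They carry the final-visit label by design.
- A reader might infer a loss of power. The documents give no missed-dose rate, so none can be claimed.

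**Conclusion.** The point holds for a missed dose 12 followed by a rating at the Week 6 visit. As written, the SAP discards an observed primary-endpoint value and imputes it, although no intercurrent-event rule calls for its removal. The imputation concerns AISRS only; the CGI-S value is left missing. The conclusion assumes that the windows are applied literally, by study day and over the nominal visit label, as SAP 2.1.3 directs. The effect is 1 of 52 primary values per affected subject, and the number of such subjects is unknown.

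The coverage sentence is wrong as a statement of fact, with limited practical effect. The missing Day 1 post-dose summary is a separate reporting gap: the data reach the listings but no by-arm table.

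**What to change.** 1. **Week 6 limit.** For AISRS and CGI-S, in subjects who have not withdrawn or permanently discontinued, set Week 6 to Day 35 through the later of Day 44 and EOT, with Week 10 from the next day. Day 44 is a proposal consistent with the date rule in SAP 10.7.2.1.1, not an existing window bound. Taking the later of the two keeps a delayed final-dose visit in Week 6.
2. **Withdrawals.** Keep early-termination visits under the final-visit label and apply the intercurrent-event rules before analysis. Mapping by study day alone would pull a Day 37 final visit after a Day 33 last dose into the MMRM.
3. **Week 2.** Give Week 2 priority over Week 10/Final for the scheduled Week 2 rating.
4. **Other rows.** Do not extend the new limit to the physical examination/ECG row. Its Week 6 window starts on Day 2, so a Day 12 final examination after a Day 8 last dose would become Week 6. If other rows are changed, apply the limit only to subjects who have not withdrawn.
5. **Coverage sentence.** Correct it in SAP 2.1.3 and state that other Day 22–34 AISRS/CGI-S ratings are listed only.
6. **COVID-19.** Reconcile SAP 10.7.2.1.1 item 1 with step 1(a) of 10.7.2.2 on whether later ratings are kept.
7. **Day 1.** Add post-dose rows (ECG at 2 hours; blood pressure and heart rate by nominal time as collected) to the windows and to the VIT, ECG and ECGTEA tables, by arm on the safety set.

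The cost is text and table edits, reprogrammed window flags and some extra table rows. No new data collection is needed.
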